### **Follow Up Assessments**

Follow up interviews are conducted by trained RAs at 1-, 2-, 3-, 4-, 6-, 9-, and 12-months post-enrollment. All sections of the assessment are interviewer-administered and entered directly into REDCap. Participants are compensated up to \$430 in gift cards throughout the study. Participants receive compensation at the end of each baseline or follow-up assessment.

## **13 Assessment of Safety and Data Safety Monitoring Plan (DSMP)**

### **13.1 Definitions for Safety Assessment**

The following definitions will be used in the assessment of safety:

*Adverse Event (AE)* is any untoward or unfavorable medical occurrence in a human subject, including any abnormal sign (for example, abnormal physical exam or laboratory finding), symptom, or disease, temporally associated with the subject's participation in the research, whether or not considered related to the subject's participation in the research.

*Serious Adverse Event (SAE)* is any adverse event that

- (1) results in death;
- (2) is life-threatening;
- (3) results in inpatient hospitalization or prolongation of existing hospitalization;
- (4) results in a persistent or significant disability/incapacity;

- (5) results in a congenital anomaly/birth defect; or
- (6) based upon appropriate medical judgment, may jeopardize the subject's health and may require medical or surgical intervention to prevent one of the other outcomes listed in this definition (examples of such events include allergic bronchospasm requiring intensive treatment in the emergency room or at home, blood dyscrasias or convulsions that do not result in inpatient hospitalization, or the development of drug dependency or drug abuse).

*Life-threatening* means that the event places the subject at immediate risk of death from the event as it occurred.

*Unanticipated Problem* is defined as an event, experience or outcome that meets **all three** of the following criteria:

- is unexpected; AND
- is related or possibly related to participation in the research; AND
- suggests that the research places subjects or others at a greater risk of harm (including physical, psychological, economic, or social harm) than was previously known or recognized.

*Possibly related* means there is a reasonable possibility that the incident, experience, or outcome may have been caused by the procedures involved in the research

*Unexpected* means the nature, severity, or frequency of the event is not consistent with either:

- the known or foreseeable risk of adverse events associated with the procedures involved in the research that are described in (a) the protocol-related documents, such as the IRB-approved research protocol (Institutional Review Board), any applicable investigator brochure, and the current IRB-approved informed consent document, and (b) other relevant sources of information, such as product labeling and package inserts; or
- the expected natural progression of any underlying disease, disorder, or condition of the subject(s) experiencing the adverse event and the subject's predisposing risk factor profile for the adverse event.

## 13.2 Safety Review

Both the risks listed in Section 4.1 and unknown risks will be monitored as follows: Adverse events and serious adverse events, including but not limited to psychological stress or discomfort from research interviews, and loss of confidentiality, will be reported by study staff (e.g., research assistants, project manager, PIs, etc) and monitored by the principal investigator. SAEs will be evaluated within 48 hours of the study staff and team becoming aware of the event for severity, seriousness, and relatedness. We have procedures and reminders in place for study staff to notify the principal investigator when an AE or SAE is reported. Additionally, we will send a yearly report to our Data Safety Monitoring Board (DSMB) who will monitor and review AEs and SAEs. The DSMB will review rates of adverse events to determine any changes in participant risk, recruitment and retention, and participant drop out, and will make appropriate recommendations for changes in protocol, which will be submitted to the Boston University Medical Campus IRB for review. A brief report will be generated yearly for the study record and forwarded to the Boston University Medical Campus IRB.

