## 4 Objectives

### 4.1 Study Objectives

The described study is a randomized clinical trial of the Treating Opioid Use, Persistent Pain, and Sadness (TOPPS) intervention compared to health education (HE) contact-control condition among

persons receiving buprenorphine for opioid use disorder. The study objectives are as follows: 1) to determine whether the TOPPS intervention, compared to HE, results in less pain interference and pain severity over the 3-month treatment phase; 2) to determine whether TOPPS, compared to HE, results in less depressive symptoms over 3 months; 3) to determine whether TOPPS, compared to HE, results in sustained improvements in pain interferences, pain severity, depressive symptoms, and buprenorphine treatment retention (self-reported continuous treatment) over the 12 months of the study. Mechanisms by which TOPPS may reduce pain interference will also be examined, including 1) (increased) activities of engagement; 2) (decreased) avoidance of meaningful life activities; and 3) (decreased) fear of pain.

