### 4.2.2 Secondary Outcome Measures

- **Depression**

The PHQ-9 (Patient Health Questionnaire-9) will be used to measure depression severity and suicidality. It is a commonly used clinical interview that yields a depression severity score between 0 and 27.

- **Buprenorphine treatment retention**

Buprenorphine treatment retention will be measured via chart review and participant self-report.

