## 6 Potential Risks and Benefits

### 6.1 Risks

There are four major areas of risk:

- **Confidentiality and loss of privacy.** Study personnel will be collecting considerable information about the study participants. This may create some distress and could cause social and psychological risk if released inappropriately. This risk is a serious one but we believe that it is highly unlikely. We have extensive experience taking measures appropriate to safeguarding confidential information.
- **Increased distress due to assessment or intervention procedures.** It is possible that some patients will experience increased intrapersonal or interpersonal psychological distress as a result of participating in assessment or intervention. Psychological risks of TOPPS may include discomfort with attention to unpleasant thoughts, feelings or body sensations. Some individual may experience an initial increase in undesirable feelings with increased attention to them. However, participants are self-guided and are encouraged to set their own limitations. In addition, the intervention is specifically geared towards dealing with such discomfort. In the vast majority of cases, we believe that any increased distress experienced will be mild and transitory in nature.
- **Ineffective intervention.** It is possible that some participants will not experience improvements in pain or depression-related outcomes OR will experience clinical deterioration or suicidality
- **Potential coercion.** It is possible that individuals may feel coerced into participating. This risk is a serious one but we believe that it is highly unlikely given informed consent processes and the ease with which one may withdraw from the study.

The following steps will be taken in order to protect and/or mitigate risk:

- **Interview:** Before conducting research assessments, participants will be assured of confidentiality and told that they have the right to terminate the interview or to refuse to answer specific questions. Some interview questions may be considered sensitive and may cause emotional distress. It will be critical to make clear to participants that they can terminate the interview at any time for any reason. The interviewer will be trained to be sensitive to signs of participant discomfort and to suggest breaks where it seems appropriate.

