## 18 Appendix

### Schedule of Events

**Table 1. Schedule of Study Measures**

Measure	Description	Baseline	Sessions	Follow-Up Assessment (Months)							
				1	2	3	4	6	9	12	
Sociodemographics Baseline	Demographic questions, including age and incarceration history	X									
Sociodemographics Follow-up	Demographic questions,	X		X	X	X	X	X	X	X	

	including places slept									
PHQ-9 	Measure of severity of depression	X	X	X	X	X	X	X	X	X
BPI 	Ratings of pain severity and interference	X	X	X	X	X	X	x	X	X
Pain Experiences 	Time ratings of least severe pain	X		X	X	X	X	X	X	X
BADS 	Measure of behavioral activation of depression	X		X	X	X	X	X	X	X
Buprenorphine and Pain - Baseline	Measures of how buprenorphine helps with pain	X								
GAD-7 	Measure of severity of anxiety	X		X	X	X	X	X	X	X
TSR – Baseline 	Compiling a list of medical appointments in the past 3 months	X								
TSR- Follow-Up 	Compiling a list of medical appointments since last follow-up			X	X	X	X	X	X	X
TRAQ 	Compiling a list of current medications	X		X	X	X	X	X	X	X
Knowledge Questionnaire	Assess patient knowledge of opioids	X								
Pain Treatment Questionnaire 	Endorsements of pain treatments	X		X	X	X	X	X	X	X

	used and ranking of their helpfulness									
IPAQ 	Measure of physical activities in the past 7 days	X		X	X	X	X	X	X	X
CPAQ 	Assess acceptance of chronic pain	X		X	X	X	X	X	X	X
PASS 	Assess anxiety around pain	X		X	X	X	X	X	X	X
PROMIS Global Health 	Assess general domains of health and functions	X		X	X	X	X	X	X	X
ASI – Baseline 	Compile lifetime use of drugs and in the last 30 days	X								
ASI – Follow-up 	Compile use of drugs in the last 30 days			X	X	X	X	X	X	X
Nicotine 	Determine cigarette use and how often	X								
DIS 	Assessing Pain sensitivity	X				X		X		X
Perceived Control Scale 	Assessing sense of agency	X			X			X		X
CPV-I 	Determine values and success living according to those values	X		X	X	X	X	X	X	X
Experience of Discrimination 	Determine history of discrimination based on identity	X								

Buprenorphine and Pain – Follow-up	Assessing buprenorphine effectiveness with pain			X	X	X	X	X	X	X	X

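### No by-arm summary of adverse events, suicidality or worsening is planned, and Section 13.2 cites the wrong section for the risks it monitors

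*Combined protocol and SAP*

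**What the plan says.** Section 13.2 states its scope as "Both the risks listed in Section 4.1 and unknown risks will be monitored as follows". Section 4.1 contains no risks. It reads "The study objectives are as follows: 1) to determine whether the TOPPS intervention, compared to HE, results in less pain interference", continues with the other objectives, and ends with the mechanisms to be examined.

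The risks are in Section 6.1, which begins "There are four major areas of risk". One is headed "Increased distress due to assessment or intervention procedures". Another, on ineffective intervention, says that some participants may not improve or "will experience clinical deterioration or suicidality".

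The examples in Section 13.2 are narrower: "psychological stress or discomfort from research interviews, and loss of confidentiality, will be reported by study staff". They are offered as a non-exhaustive list. The principal investigator monitors events as they are reported, and the DSMB receives a yearly report and reviews adverse-event rates. Section 13.3 has the IRB receive a summary at continuing review that judges the pattern of events as a whole. Neither section mentions study arm.

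Section 4.2.2 says the PHQ-9 "will be used to measure depression severity and suicidality". Section 15.3 and Table 1 schedule the PHQ-9 and BPI at baseline and at every follow-up. Section 15.3 models pain interference, pain severity and depressive symptoms by treatment. It contains no safety analysis.

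**The concern.** In this population a harmful effect of the intervention would be hard to recognise one case at a time. Section 6.1 says every participant has risk factors for suicidality, and Section 6.2 treats that risk as inherent in the population. Section 13.1 counts an event as expected when it fits the underlying condition and the participant's risk profile. An excess caused by treatment would therefore show mainly as a difference between arms, and the plan does not set out that comparison for events, for suicidality or for individual worsening.

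The question is a fair one for this intervention. Section 12 tells TOPPS participants that working towards goals can be worthwhile even if pain or discomfort rises for a time. A favourable mean difference in pain or PHQ-9 could coexist with a subgroup that gets worse, and a model of the PHQ-9 total does not isolate question 9.

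**Working it through.** **Step 1. Set the sections side by side.** The plan states no figure on this point, so there is none to reproduce.

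| Harm | Named in 6.1 | Among the 13.2 examples | Route for individual cases | By-arm summary planned |
|---|---|---|---|---|
| Suicidality | Yes | No | Screening and escalation procedure in 6.1, with a written record | No; 15.3 models depressive symptoms, not question 9 |
| Clinical deterioration | Yes | No | May be recorded under the broad definition in 13.1 | Mean scores only (15.3) |
| Distress from the intervention | Yes | No | May be recorded under 13.1 | No, and Table 1 has no dedicated measure |
| Distress from assessments | Yes | Yes | Staff report | No |
| Loss of confidentiality | Yes | Yes | Staff report | No |

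Two gaps follow. First, no rule says when a positive suicide screen or a deterioration becomes an adverse event and so reaches the DSMB. Second, no by-arm summary is planned for adverse events, suicidality or the proportion worsening.

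**Step 2. Check that the data are scheduled.** The PHQ-9 (including question 9) and the BPI are given by research assistants to both arms on the same calendar. Section 6.1 already supplies a criterion for significant suicide risk: a PHQ-9 total of at least 18, any score above 0 on question 9, or telling staff of a wish or intent to harm oneself. It also requires every suicide assessment to be written up. A by-arm table therefore needs no new data collection.

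**Step 3. Work out the precision such a table would have.**

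Inputs:
- Section 2 gives 163 randomised and Section 5 gives 1:1 allocation: 163 / 2 = 81.5, taken as 81 per arm.
- Section 15.2 assumes 20% attrition: 81 × 0.80 = 64.8, taken as 65 per arm.
- The documents give no event rates. The values of p below are assumptions, taken as equal in the two arms.

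The 95% half-width for a risk difference is 1.96 × √(2p(1 − p)/n). For example, at p = 0.10 and n = 81 it is 1.96 × √(0.18/81) = 1.96 × 0.0471 = 0.092. At p = 0.20 and n = 65 it is 1.96 × √(0.32/65) = 1.96 × 0.0702 = 0.138.

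| Assumed rate p | Half-width, 81 per arm | Half-width, 65 per arm |
|---|---|---|
| 5% | 6.7 points | 7.5 points |
| 10% | 9.2 | 10.3 |
| 15% | 11.0 | 12.3 |
| 20% | 12.3 | 13.8 |
| 30% | 14.1 | 15.8 |

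**Step 4. Check power, to see whether the table could be more than descriptive.** For 10% against 20% with 81 per arm and a two-sided 5% test:
- Standard error under the null: √(2 × 0.15 × 0.85/81) = 0.0561.
- Standard error under the alternative: √((0.09 + 0.16)/81) = 0.0556.
- z = (0.10 − 1.96 × 0.0561)/0.0556 = −0.18, so power is about 43%.

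On the same basis, power to detect a doubling is about 23% from a 5% rate, 80% from 20% and 98% from 30%. Unless these harms are common, the table can only describe.

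**The case against.** The strongest reply is that the protocol already provides for these harms. Much of that stands.

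- **A reader might infer that suicidality and deterioration are never reviewed.** The documents do not support that. The examples in Section 13.2 are open-ended and the section also covers unknown risks. The definition in Section 13.1 takes in any untoward medical occurrence or symptom, related or not. The DSMB reviews adverse and serious adverse events. Section 6.1 sets out a suicidality procedure with senior review and access to a clinician.
- **A reader might infer that nothing is compared by arm.** Section 15.3 compares mean pain and PHQ-9 scores with two-tailed tests at 3 months and at later visits, so average worsening under TOPPS would be estimated. The gap is confined to adverse events, suicidality and the proportion worsening.
- **A reader might infer that complete data exist for every named harm.** Attrition of 20% is expected, and the 12-month visit applies only to those enrolled before October 2023. Intervention distress has no dedicated measure. The treatment-services follow-up form is described only as "Compiling a list of medical appointments since last follow-up", which does not establish that it captures hospital contacts.
- **A reader might suspect that staff reports rise with session attendance and so bias the arm comparison.** Nothing in the documents shows this. Both arms are offered six sessions of the same timing and length, with the same questionnaires.

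The documents also do not exclude that the DSMB already sees data by arm; no charter is included. Section 2 describes randomisation in the past tense, so a change to DSMB reports may come late. The analysis gap in Section 15.3 remains whatever the DSMB sees.

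**Conclusion.** The point holds in a limited form. The citation of Section 4.1 is a clerical error and the omitted examples are missing detail; neither would matter much alone. The substantive gap is that the planned analysis yields no between-arm estimate for adverse events, suicidality or individual worsening. The plan itself says the PHQ-9 measures suicidality and gives it to both arms on one schedule.

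If the gap is filled, the half-width would be about 9 to 12 points at 81 per arm, or about 10 to 14 at 65 per arm. This rests on assumed rates of 10% to 20%, equal arms, and attrition as Section 15.2 expects. The true rates could lie outside that range, since all participants enrol with depressive symptoms. The table could reveal a large excess but could not rule out a moderate one. It is a cheap improvement, not a repair to the primary analysis.

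**What to change.** 1. In Section 13.2, change the reference to Section 6.1. Name suicidality, clinical deterioration and intervention-related distress among the examples, and state how they enter the adverse-event record.
2. In Section 15.3, add a descriptive by-arm safety table from the scheduled research assessments and the suicide-assessment records. Give the number assessed, the number with the event, the risk difference and its 95% confidence interval for:
   - PHQ-9 question 9 above 0, shown by baseline status so that new ideation is separated from existing ideation;
   - the protocol's own Section 6.1 criterion for significant suicide risk;
   - documented suicide assessments;
   - worsening from baseline in PHQ-9 and in BPI, with the definition of worsening set by the investigators before data are seen by arm.
3. State the follow-up window for each row, because the 12-month visit is not scheduled for everyone.
4. List staff-reported adverse and serious adverse events by arm in a separate table.
5. Provide both tables to the DSMB as a closed report, and say in Section 13.2 that it reviews them by arm.

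The clinical thresholds and the management of suicidality are left as they are. The cost is protocol and SAP wording and a small amount of analysis of data already being collected. The downside is that the DSMB report becomes a closed by-arm report, which must be kept from staff who should not see results by arm.

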Given that all participants will have risk factors for suicidality (i.e., chronic pain and elevated depressive symptoms), some participants may experience suicide ideation or behavior in the course of study participation. Significant risk for suicide will be defined by PHQ-9 total score of 18 or greater, a score of greater than 0 on question 9 of PHQ-9 (both indicating suicide ideation or intent or behavior), OR the report of a desire or intent to hurt oneself to study staff. All staff members will be trained by [name] on the study's Suicide Ideation Protocol. Details on the procedural steps will be included in the study's Standard Operating Procedures (SOP), a copy of which all Research Assistants have with them at all times. The Suicide Ideation SOP details key warning signs and/or language of a participant with possible suicidal or homicidal thoughts and procedures for next steps. If a staff member encounters an individual who endorses suicide or homicide ideation, they will use the MSSI (Modified Scale for Suicidal Ideation) to ask a series of follow up questions to determine if a participant has a plan to hurt themselves or others, if they have tried to do so in the past, and if they have access to a specific method of self-harm. Following this brief discussion, the research member will immediately call a senior staff member to review the participant's responses and determine if immediate action is necessary. Each site will have at least two licensed clinicians identified to assist with study participants who endorse harming themselves or others. This individual will be called and/or paged and will reach out to the participant immediately for evaluation. When a clinician is asked to conduct an immediate evaluation, he or she will conduct a suicide risk assessment. The clinician will determine whether it is necessary to take immediate action to prevent the participant from causing harm to him/herself. If the participant is not in immediate danger of hurting him or herself, we will take the following actions. First, we will inform the patient about procedures for contacting emergency services should they find themselves at risk for self-harm. Second, with the patient's permission, we will contact their primary care physician or other clinician to inform them of the suicidality. We will urge the patient to make an appointment with that provider to discuss treatment options. Third, if the patient consents, we will speak with one of their family members to ensure that he/ she is aware of the seriousness of the patient's symptoms and the agreed-upon treatment plan. We will provide treatment referrals if the patient wishes. Regardless of outcome, suicide assessments are always documented in writing.

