## 6.2 Potential Benefits

From a societal standpoint, this research endeavor could lead to the incorporation of a theoretically-driven and effective behavioral health treatment for patients with pain and depression into OUD care. This would be the first large-scale study of behavioral health treatment for chronic pain in people with OUD. We believe that this treatment will lead to improved pain, depression, and OUD outcomes. The risks of suicide or homicide are inherent in this patient population. All participants may acquire an increased awareness of their connections between pain and depression, and how these connections may relate to their OUD care plan. Participants assigned to the Life Goals intervention may further benefit by developing pain and mood management skills. Participants assigned to the HE intervention may benefit by increasing their knowledge of general health issues. Given that the risks of participation are fairly low, the risks to participants are judged to be acceptable relative to the anticipated benefits.

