## 13.3 Reporting Plans

The Principal Investigator at BMC/BU Medical Campus will report Unanticipated Problems, safety monitors' reports, and Adverse Events to the BMC/BU Medical Center IRB in accordance with IRB policies:

- Unanticipated Problems occurring at BMC/BU Medical Campus will be reported to the BMC/BU Medical Campus IRB within 7 days of the investigator learning of the event.
- Adverse Events (including Serious Adverse Events) will be reported in summary at the time of continuing review, along with a statement that the pattern of adverse events, in total, does not suggest that the research places subjects or others at a greater risk of harm than was previously known.
- Reports from safety monitors with recommended changes will be reported to the IRB within 7 days of the investigator receiving the report.
- Reports from safety monitors with no recommended changes will be reported to the IRB at the time of continuing review.

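### A death, suicide attempt or other life-threatening event judged expected or unrelated has no stated prompt route to the IRB or DSMB, and the IRB summary has its conclusion fixed in advance

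*Combined protocol and SAP*

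**What the plan says.** **Routes to independent reviewers.** Under Section 13.3, Unanticipated Problems go to the IRB within 7 days. Other adverse events, serious ones included, go to it in summary at continuing review, "along with a statement that the pattern of adverse events, in total, does not suggest that the research places subjects or others" at more risk than was known before. Section 13.2 adds a brief yearly report to the IRB and, for the board, says "we will send a yearly report to our Data Safety Monitoring Board (DSMB) who will monitor and review AEs and SAEs". A safety-monitor report that recommends changes is passed to the IRB within 7 days. Section 13.3 places all this under IRB policies, which the document does not reproduce.

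**Internal step.** Under 13.2, SAEs are evaluated within 48 hours for severity, seriousness and relatedness, and the principal investigator monitors them.

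**Definitions.** In 13.1 an Unanticipated Problem must meet three conditions together: unexpected, related or possibly related, and suggestive of greater risk than was recognized. Whether an event is unexpected is judged on nature, severity or frequency against two benchmarks. One is the foreseeable risk of the research procedures as described in the protocol and related documents. The other is the natural course of the condition and the subject's "predisposing risk factor profile for the adverse event".

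**Suicidality.** Section 6.1 says that "all participants will have risk factors for suicidality (i.e., chronic pain and elevated depressive symptoms") and that "some participants may experience suicide ideation or behavior in the course of study participation". Under ineffective intervention, it also lists the possibility that participants "will experience clinical deterioration or suicidality". Section 6.2 says "The risks of suicide or homicide are inherent in this patient population".

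**Stopping rules.** Section 13.4 states that none are pre-defined.

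**The concern.** In this population the most serious foreseeable event is a suicide attempt or a death. The protocol's description of the population supplies the grounds for calling such an event expected, and an expected event cannot take the 7-day route. The two bodies independent of the study team would then learn of it only through periodic summaries, unless policies outside the document require more.

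The second issue stands apart from timing. A continuing-review summary should tell the IRB what the accumulated events show. Section 13.3 specifies what it will conclude.

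At stake is whether someone outside the team, with arm available, looks at the gravest events soon enough to act. Section 6.1 accepts that the intervention may at first increase undesirable feelings, so an imbalance between arms would be informative. With no pre-defined stopping rules, the judgment of the DSMB and IRB carries the independent part of the monitoring.

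**Working it through.** The plan gives no figure to reproduce. The check follows a suicide attempt through the definitions and routes, then sets out the reporting intervals.

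1. **Is it unexpected?** The 13.1 test turns on inconsistency with either benchmark, which can be read two ways.
   - If fitting one benchmark is enough to make an event expected, the second suffices, because 6.1 attributes risk factors for suicidality to every participant.
   - If both must fit, the first can also be argued, because 6.1 lists suicidality among the study's risks. This is the weaker limb: it concerns risks of the research procedures, and 6.1 places suicidality under ineffective intervention.
   - Severity does not clearly rescue the event, since 6.1 foresees behavior as well as ideation and 6.2 names suicide.
   - Frequency could, but no expected rate is given to compare with.

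   An attempt can therefore be judged expected. It need not be.

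2. **Is it related, and does it suggest greater risk?** Both are also required. An attempt judged unrelated, or not suggestive of greater risk, misses the 7-day route however expectedness is decided.

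3. **Who decides expectedness, and when?** The 48-hour evaluation does not list it, and no other step is named.

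4. **Does the 7-day rule cover every participant?** As worded, it refers to problems occurring at BMC/BU Medical Campus. Section 9.1 also recruits from SSTAR and through advertising.

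5. **What is left if any condition fails?**

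| Recipient | Stated route | Stated interval |
|---|---|---|
| IRB | Summary at continuing review (13.3) | Not given |
| IRB | Brief report (13.2) | Yearly |
| DSMB | Report covering AEs and SAEs (13.2) | Yearly |

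   No expedited SAE notice to the DSMB is described.

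6. **Summary statement.** Section 13.3 gives one form of words, with no alternative for a pattern that does suggest greater risk.

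7. **Scale.** Inputs: a yearly DSMB report, taken as 365 days (13.2); the 7-day clock (13.3); and a treatment phase of 12 weeks (Section 2), 12 × 7 = 84 days. Assume that events fall evenly over the year and ignore delays in reporting and preparation.
   - Longest wait for the DSMB: 365 days; 365 / 7 ≈ 52 times the 7-day clock.
   - Mean wait: 365 / 2 = 182.5 days, about 6 months.
   - Mean wait relative to the treatment phase: 182.5 / 84 ≈ 2.2.

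**The case against.** **Participants are not left unprotected.** A reader might infer that yearly review is the only safeguard, or that people in treatment cannot be protected. The documents do not support that. Section 6.1 sets PHQ-9 triggers, structured follow-up questions, an immediate call to senior staff, clinician evaluation and written documentation. The PHQ-9 is scheduled at every follow-up, suicidality needing immediate attention is an exclusion, and SAEs are evaluated within 48 hours. This stands and confines the point to independent oversight.

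**The definitions do not force the outcome.** A reader might infer that every attempt will be filed as expected, or that expectedness alone decides. Neither follows: an investigator could call an attempt, or a cluster of them, unexpected, and two other conditions also apply. The weakness is that the outcome is left to discretion for the gravest events.

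**Unseen documents may close the gap.** IRB policies or a DSMB charter could require prompt notice, and continuing review need not be annual. This stands as a caveat. The safety section should still state its own route.

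**The summary statement may be only an attestation.** A worrying pattern might already have been reported as an Unanticipated Problem, and DSMB recommendations for change reach the IRB within 7 days. But a pattern of events each judged expected would fail the first condition, and the only DSMB input described is the yearly report. The wording remains one-sided.

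**The waiting times are not data.** They follow from an assumed even spread of events, and nothing shows that earlier looks would detect a difference between arms. They indicate scale only.

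**It may be late.** Section 2 reports that 163 participants were randomized, so enrollment appears complete. The timing change would then matter mainly for remaining follow-up and the final safety review. The wording change applies regardless.

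**Conclusion.** The point holds as one about independent oversight. On the stated text, a death, suicide attempt or other life-threatening SAE is sure of a 7-day IRB report only if it passes three judgments, and the protocol makes it easy for a suicide attempt to fail at least one. The independent review that then remains is periodic, and for the DSMB it is yearly. Under an even spread of events, that means a mean wait of about 6 months and a longest wait of about 12, against a 12-week treatment phase. Separately, 13.3 fixes the conclusion of the IRB summary. That finding rests on the wording alone and needs no assumption.

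The conclusion on timing assumes that the unseen IRB policies, and any DSMB charter, add no faster duty. It does not show that any event was mishandled or that clinical care is deficient. It is an inexpensive improvement worth making.

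**What to change.** - **Section 13.2:** after the existing 48-hour evaluation, send every death, suicide attempt and other life-threatening SAE to the DSMB, with arm available to it, and to the IRB, within the 7 days already used for Unanticipated Problems. Apply this regardless of expectedness or relatedness and wherever the participant was recruited.
- **Section 13.3:** replace the fixed wording with a statement of whether the pattern of adverse events suggests greater risk than was previously known. The DSMB makes the by-arm assessment.
- **If IRB policy or a DSMB charter already requires such notice,** cite it in 13.2.
- **In the same edit,** correct the pointer in 13.2 to risks in Section 4.1, which holds the study objectives; the risks are in 6.1.

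The cost is protocol wording, a small added reporting step and a few extra notifications. The 48-hour and 7-day clocks are the protocol's own. Clinical management, eligibility and the efficacy analysis are unchanged.
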